#### 8.6.7      Electrocardiograms

Subjects must be resting quietly in a supine position or in the most recumbent position possible for at least 5 minutes before the ECG is obtained. The following ECG parameters will be recorded: HR, RR, PR, QRS, and QT and QT interval corrected for HR using Fridericia's formula (QTcF) intervals.

Electrocardiogram assessment will include interpretation of the tracings, eg, rhythm, presence of arrhythmia or conduction defects, morphology, any evidence of myocardial infarction, or ST segment, T-wave, and U-wave abnormalities. The investigator or designee is responsible for reviewing and over-reading the ECG interpretation, for assessing whether the ECG machine interpretation findings are accurate, appropriate, normal or abnormal, and for providing corrected interpretations as appropriate. In addition, any abnormal ECGs will be assessed for clinical significance.

Additional ECGs may be obtained if clinically indicated. Any additional relevant data obtained by the investigator during the course of this study will be supplied to the sponsor.

For any ECG that the investigator considers clinically significant, the investigator will:

- Repeat the ECG.
- Follow-up ECG(s) will be obtained if any significant abnormalities are detected after dose administration to document resolution and as clinically indicated.
- Record as an AE any ECG that (1) is confirmed and the investigator considers clinically significant, (2) requires a subject to be discontinued from the study, (3) requires a subject to receive treatment, or (4) requires a change or discontinuation of the study drug (if applicable).

#### 8.6.8      Appropriateness of Safety Assessments

Safety evaluations selected for this study are typical of those for this subject population and utilize widely accepted measures.

A crash cart containing epinephrine will be available for each dosing event throughout the study.

CONFIDENTIAL

## **9 ADVERSE EVENTS**

An AE is defined as any untoward medical occurrence in a subject administered a pharmaceutical product during the course of a clinical investigation. An AE can therefore be any unfavorable and unintended sign, symptom, or disease temporally associated with the use of an investigational product, whether or not thought to be related to the investigational product.

Subjects will be monitored throughout the study for AEs, from administration of the first dose of study drug through the EOS visit. Adverse events that are identified at the last assessment visit (or the early termination visit) as specified in the protocol must be recorded on the AE eCRF with the status of the AE noted. All events that are ongoing at this time will be recorded as ongoing on the eCRF. All (both serious and nonserious) AEs must be followed until they are resolved or stabilized, or until attempts to determine resolution of the event are exhausted. The investigator should use his/her discretion in ordering additional tests as necessary to monitor the resolution of such events.

The procedures specified in [Section 9.4](#) are to be followed for reporting SAEs.

### **9.1 Recording Adverse Events**

Adverse events are to be recorded on the AE page of the eCRF. The following information will be recorded:

- Assessment of whether or not the AE is a SAE ([Section 9.2.1](#))
- Assessment of AE intensity ([Section 9.2.2](#))
- Assessment of AE relationship to study drug ([Section 9.2.3](#))
- Action taken - categorized as none, study drug discontinued, dose modified, required concomitant medication, required procedure, or other
- Outcome - recorded as event resolved, resolved with sequelae, ongoing, or death

### **9.2 Assessment of Adverse Events**

The investigator will assess each AE for seriousness, intensity, and relationship to study drug.

CONFIDENTIAL

### 9.2.1 Serious Adverse Events

The investigator is responsible for determining whether an AE meets the definition of a SAE. A SAE is any AE occurring from ICF signing through the EOS visit that results in any of the following outcomes:

- Death
- A life-threatening adverse drug experience
- Inpatient hospitalization or prolongation of existing hospitalization
- A persistent or significant disability/incapacity
- A congenital anomaly/birth defect

Important medical events that may not result in death, be life-threatening, or require hospitalization may be considered a SAE when, based upon appropriate medical judgment, they may jeopardize the subject and may require medical or surgical intervention to prevent any of the outcomes listed in this definition. Examples of such medical events include allergic bronchospasm requiring intensive treatment in an emergency room or at home, blood dyscrasias or convulsions that do not result in inpatient hospitalization, or the development of drug dependency or drug abuse.

Note: SAEs require immediate reporting to the medical monitor. Refer to “Reporting Serious Adverse Events” ([Section 9.4](#)) for details.

### 9.2.2 Intensity

The intensity of an AE will be graded according to the following definitions:

- Mild: Any symptom of which the subject is aware, but which is easily tolerated; asymptomatic or mild symptoms; clinical or diagnostic observations only; intervention not indicated.
- Moderate: Any symptom which is discomforting enough to cause interference with a subject's usual activity; minimal, local, or noninvasive intervention indicated; limiting age-appropriate instrumental activities of daily living (ADL).
- Severe: Any symptom which causes a subject's inability to perform usual activity; severe or medically significant but not immediately life-threatening; hospitalization or prolongation of hospitalization indicated; disabling; limiting self-care ADL.

CONFIDENTIAL

### 9.2.3 Relationship to Study Drug

The relationship of an AE to the study drug should be determined by the investigator according to the following criteria:

- Not related: The event is most likely produced by other factors such as the subject's clinical condition, intercurrent illness, or concomitant drugs, and does not follow a known response pattern to the study drug, or the temporal relationship of the event to study drug administration makes a causal relationship unlikely
- Possibly related: The event follows a reasonable temporal sequence from the time of drug administration, and/or follows a known response pattern to the study drug, but could have been produced by other factors such as the subject's clinical condition, intercurrent illness, or concomitant drugs
- Probably related: The event follows a reasonable temporal sequence from the time of drug administration, and/or follows a known response pattern to the study drug, and cannot be reasonably explained by other factors such as the subject's clinical condition, intercurrent illness, or concomitant drugs

### 9.2.4 Significant Adverse Events

Significant AEs are defined as marked hematological and other laboratory abnormalities (other than those meeting the definition of serious) and any events that led to an intervention, including withdrawal of study drug, dose reduction, or significant additional concomitant therapy, other than those reported as SAEs.

## 9.3 Discontinuation due to Adverse Events

Any subject who experiences an AE may be withdrawn at any time from the study at the discretion of the investigator. Subjects withdrawn from the study due to an AE, whether serious or nonserious, may be followed by the investigator until the clinical outcome of the AE is determined. The AE(s) should be noted on the appropriate eCRFs and the subject's progress should be followed until the AE is resolved or stabilized as determined by the investigator. The medical monitor must be notified. If the AE relates to overdose of study treatment, the Investigator's Brochure should be consulted for details of any specific actions to be taken.

## 9.4 Reporting Serious Adverse Events

In the event of any SAE reported or observed during the study, whether or not attributable to the study drug, site personnel will report it immediately by telephone to the medical monitor AND to the SAE hotline at ICON in accordance with procedures described in the study reference manual and/or SAE study-specific procedure. Site personnel will follow up with a faxed written report on the next working day as follows.

CONFIDENTIAL

**ICON SAE Hotline [contact]**

**This telephone report must be followed within 24 hours by a FAX transmission of a completed SAE Report Form to the number indicated below:**

**[contact]**

SAE Report Forms will be provided to the investigational site to assist in collecting, organizing, and reporting SAEs and follow-up information.

All SAEs should be followed to their resolution, with documentation provided to ICON on a follow-up SAE Report Form.

#### **9.5        Pregnancy**

The investigator must report any pregnancy to the medical monitor and to the ICON Medical and Safety Service within 1 business day of becoming aware of the pregnancy per pregnancy reporting procedures described in the study reference manual. An uncomplicated pregnancy will not be considered an AE or SAE; however, all pregnancies will be followed through birth and 3 months postdelivery.

Pregnancies in the sexual partners of male subjects will be captured from the time the subject is first exposed to the investigational product until 90 days after last exposure to the investigational product.

Any congenital abnormalities in the offspring of a subject who received study drug will be reported as a SAE. The outcome of any pregnancy and the presence or absence of any congenital abnormality will be recorded in the source documentation and reported to the medical monitor and sponsor.

#### **9.6        Drug-induced Liver Injury**

Subjects will be monitored for signs of drug-induced liver injury (DILI). Study drug will be withheld in the event of potential DILI.

Potential events of DILI will be defined as meeting all of the following criteria (as specified in the [FDA Guidance for Industry Drug-induced Liver Injury: Premarketing Clinical Evaluation, 2009](#)):

- Alanine aminotransferase or aspartate aminotransferase  $> 3 \times$  ULN
- Total bilirubin  $> 2 \times$  ULN without initial findings of cholestasis (elevated serum alkaline phosphatase)
- No other reason can be found to explain the combination of laboratory value increases (eg, acute viral hepatitis; alcoholic and autoimmune hepatitis; hepatobiliary disorders; nonalcoholic steatohepatitis; cardiovascular causes; concomitant treatments)

CONFIDENTIAL

FAST BioMedical  
Protocol Number: 36770001  
Final Protocol 1.1

Potential events of DILI will be reported as SAEs ([Section 9.4](#)). All subjects with potential DILI will be closely followed until abnormalities return to normal or baseline or until all attempts to determine resolution of the event are exhausted.

CONFIDENTIAL

July 17th, 2017 Version 1.1 Monday, July 24, 2017  
Page 70 of 81

## **10 STATISTICAL CONSIDERATIONS**

The statistical analysis will be conducted following the principles as specified in International Council for Harmonisation (ICH) Topic E9 (CPMP/ICH/363/96).

All statistical analyses will be described in a separate SAP.

### **10.1 Sample Size Calculation**

Approximately 32 subjects/patients will be enrolled in 4 cohorts consisting of up to 8 subjects/patients each.

The sample size in this study is representative of Phase 2b studies of this type. Power calculations were not used to derive the sample size.

### **10.2 Analysis Populations**

Pharmacokinetic Full Population: All subjects in Cohorts 2 through 4 who receive a known amount of study drug and have at least one quantifiable concentration of FD001 or FD003 in plasma or FD001 in urine and subjects in Cohort 1 who receive a known amount of study drug. Plasma concentrations for subjects in Cohort 1 will not contribute to the overall PK statistical analysis and will be analyzed for  $CL_r$ ,  $C_{max}$ , and using the FAST mGFR and PV measurement calculations only.

Pharmacokinetic Evaluable Population: All subjects in Cohorts 1 through 4 who receive a known amount of study drug and have at least 1 estimable PK parameter.

Safety Population: All subjects who received any amount of study drug.

Pharmacodynamic Evaluable Population: All subjects in Cohorts 1 through 4 who have either a PV or GFR estimate using any of the techniques under study. Subjects in Cohort 1 will not contribute to the overall PD statistical analysis.

CONFIDENTIAL

### **10.3 Endpoints**

#### 10.3.1 Primary Endpoints

##### 10.3.1.1 Safety

- AEs and SAEs
- Clinical laboratory tests, physical examination findings, 12-lead EGs, and vital signs including pulse oximetry

##### 10.3.1.2 Pharmacokinetics

- $C_{max}$
- $t_{max}$
- $AUC_{0-12}$  (FD001 only)
- $AUC_{last}$
- $AUC_{inf}$
- $t_{1/2}$
- $\lambda_z$
- CL
- $CL_{r0-2}$  (FD001 only)
- $CL_{r2-12}$  (FD001 only)
- $CL_{r0-12}$  (FD001 only)
- $V_z$
- $V_{ss}$
- $Ae_{0-2}$
- $Ae_{2-12}$
- $Ae_{0-12}$

#### 10.3.2 Secondary Endpoints

##### 10.3.2.1 Pharmacodynamic

- PV as assessed by FAST PV and mGFR Technology
- PV as assessed by Nadler's formula
- Assess changes in PV after fluid challenge
- Assess repeatability of GFR measurements over 24 hours
- mGFR as assessed by FAST VFI and Iohexol clearance methods

CONFIDENTIAL

- eGFR (calculated by MDRD, CKD-EPI, and Cockcroft-Gault equations)

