Both Iohexol and the FAST mGFR technologies utilized timed blood draws and subsequent concentrations to calculate a predicted total AUC. The dose of marker given was divided by this AUC to calculate the mGFR, with scaling based on body surface area. The FAST mGFR utilized 3 blood draws taken at early time points out to 2 hours. A fourth virtual point was calculated based on the PV at T0 (the starting concentration in the plasma just after the dose is given or time 0). The Iohexol GFR 6 test utilized a blank, plus a minimum of 6 additional blood draws taken over 6 hours to determine the AUC. Iohexol, having a much smaller molecular size, distributes differently within the extracellular space, so some difference in mGFR between the 2 markers was anticipated. FAST BioMedical expected to measure mGFR values slightly lower than Iohexol in normal patients, as most single marker systems like Iohexol have difficulty resolving the early decay phase when the clearance is rapid. It was expected that the FAST mGFR measurements would be within 10% in the lower GFR groups. Prior studies conducted by FAST BioMedical using both the VFI and Iohexol in anesthetized dogs, have shown there were differences between the 2 methods. Analysis of the single marker decay rate showed that it normally resolved to a falsely high volume of distribution making the resulting mGFR biased higher than the FAST 2 marker system, which quantifies the initial volume of marker distribution. This small error in AUC was only significant in mGFRs above 80 mL/min.

In addition to studying a range of GFRs using different measurement techniques, FAST BioMedical intended to evaluate FAST’s measured PV method against a standard clinical estimate of PV, specifically Nadler’s Formula (Nadler et al 1962).

$$\text{Plasma Volume (males)} = 0.3669 \times (\text{Height [m]})^3 + 0.03219 \times (\text{Body Weight [kg]}) + 0.6041$$

$$\text{Plasma Volume (females)} = 0.3561 \times (\text{Height [m]})^3 + 0.03308 \times (\text{Body Weight [kg]}) + 0.1833$$

CONFIDENTIAL

The difference between a measured and estimated PV are between plus 20% to minus 30% ([Feldschuh and Enson, 1977](#)) using radioiodinated human serum albumin as the measured plasma marker. Since Nadler's work was based primarily on measurements in healthy subjects, it was expected there may be a greater range seen with the CKD population in this study.

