## **4 OBJECTIVES**

### **4.1 Primary Objectives**

- To assess the safety and tolerability of VFI (employing the FAST PV and mGFR Technology) compared to Iohexol (employing Iohexol clearance methods) in healthy subjects and patients with impaired renal function
- To evaluate the PK of FD001 and FD003 in healthy subjects and patients with impaired renal function
- To evaluate the PK of FD001 and FD003 in healthy subjects receiving 2 doses of VFI separated by 24 hours to evaluate the reproducibility of the FAST mGFR Technology

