Ae 0-12	Amount of FD001 excreted unchanged in urine from time 0 to 12 hours

CONFIDENTIAL

Extrapolation methods will be used in Cohort 2, as needed, to correct concentration data after a second dose of FAST VFI in order to calculate PK parameters. Alternative methods (ie, compartmental modeling) may be used if extrapolation methods are inadequate. Computational details will be provided in a separate statistical analysis plan (SAP).

For the calculation of the FAST mGFR and PV in Cohort 2, residual levels of FD003 will be measured in the predose sample and those values subtracted from post-second-administration sample values to allow for a clean calculation of PV from dose 2. As these are healthy subjects we are not anticipating any level of residual FD001 that would affect the calculation of GFR.

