#### **10.5 Pharmacodynamic Statistical Analysis**

##### **10.5.1 Plasma Volume**

The FAST PV Technology for determining PV will be compared to PV estimated using Nadler's formula. Plasma volume data will be listed and summarized by presenting descriptive statistics of raw data. The correlation as well as the associated plot will be presented for comparing PV between methods. [Cosgriff et al. 1999](#) shows that a combination of the correlation and a histogram of the magnitude of difference is needed when no measured comparator is available.

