10.1.10 Analysis of Pharmacodynamic Data

10.1.10.1 Plasma Volume (PV)

The FAST PV Technology plasma volume (PV) will be compared to PV estimated using Nadler's formula. Plasma volume data will be listed and summarized by presenting descriptive statistics of raw data and for change in plasma volume.

Correlation analysis will be done for comparing the PV measured using FAST PV method and PV estimated using Nadler's Formula for each cohorts. Pearson product-moment correlation coefficient, standard error with 95% confidence interval of the coefficient will be provided.

In addition scatter plot will also be provided to support the correlation analysis. Also, histogram will be provided for the magnitude of difference (PV using FAST PV - PV estimated using Nadler's formula).

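### Cohort 2 gives two FAST plasma volumes per subject 24 hours apart, but no endpoint or listed output compares them, so the plan cannot describe how reproducible FAST PV is across doses

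*Protocol*

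**What the plan says.** Cohort 2 (up to 8 healthy subjects) receives VFI on Day 1 and again 24 hours later. Protocol Sections 3.6.1 and 8.4.2 explain that FD003 left from dose 1 is measured in the Day 2 predose sample and "subtracted from post-second-administration sample values to allow for a clean calculation of PV from dose 2". Every completing subject therefore has two FAST PVs.

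The secondary endpoints in Protocol 10.3.2.1 and SAP 5.4.1 include "Assess repeatability of GFR measurements over 24 hours". They contain no counterpart for PV. Protocol 7.3 gives mGFR repeatability as the purpose of the second dose.

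The PV analysis (Protocol 10.5.1, SAP 10.1.10.1) consists of descriptive statistics, a correlation and scatter plot against Nadler's formula, and a histogram of FAST minus Nadler. The protocol says that the correlation and histogram are both "needed when no measured comparator is available". The SAP adds: "Plasma volume data will be listed and summarized by presenting descriptive statistics of raw data and for change in plasma volume". It does not say between which measurements the change is taken. SAP Section 11 lists one PV table, one PV scatter plot and one PV histogram, and none is described as Day 1 against Day 2.

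PV also enters the mGFR. Protocol 3.3 states the principle that the FD001 decline is combined with the PV from FD003. For Phase 2a, Section 3.4.3 reports: "A fourth virtual point was calculated based on the PV at T0".

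**The concern.** Agreement with Nadler's formula does not measure the precision of FAST PV. Protocol 3.4.3 puts the difference between a measured and an estimated PV at +20% to -30%, so scatter around Nadler mixes the formula's error with that of FAST. The Day 1/Day 2 pair is the one place where the trial repeats the whole PV procedure (new injection, new samples) in the same subject, and the plan does not use it.

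Two things are at stake. The report will have no statement on how far two FAST PVs in one subject may differ across doses, although Protocol 3.6.1 expects repeat dosing in practice. And Day 2 PV carries extra error from the residual subtraction, which helps in reading any Day 2 shift in mGFR, yet no output summarises it.

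**Working it through.** **Plan figures.** The sample size is 4 × 8 = 32: "Approximately 32 subjects/patients will be enrolled in 4 cohorts consisting of up to 8 subjects/patients each". Also, "Power calculations were not used to derive the sample size". The plan gives no precision or repeatability figure that could be reproduced.

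**Inputs from the documents**
- FD003 half-life in healthy subjects: 47 to 111 h across doses in the first-in-human study (Protocol 3.4.2) and 90 h in Phase 2a (3.4.3).
- Dosing interval: 24 h. There is one Day 2 predose sample (Table 2.5).
- At most 8 pairs.

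**Assumptions**
- Independent proportional assay error a. The documents do not give it; 2% to 8% is used.
- The same PV and dose on both days, with decay during the sampling window ignored.
- m = 1 post-dose sample, or m = 3 averaged. The plan does not say how many samples feed the PV; three draws is the number described for the Phase 2a mGFR.

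**Residual.** r = 0.5^(24/h): 0.70 at 47 h, 0.83 at 90 h, 0.86 at 111 h.

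**Error of each PV.** Set the concentration after dose 1 to 1. After dose 2 the total is 1 + r, and the net value after subtracting r is 1.
- Day 1: CV = a/√m
- Day 2: CV = a·√[(1 + r)²/m + r²]

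| Half-life | r | Day 2/Day 1 error, m = 1 | Day 2/Day 1 error, m = 3 |
|---|---|---|---|
| 47 h | 0.70 | 1.84 | 2.09 |
| 90 h | 0.83 | 2.01 | 2.33 |
| 111 h | 0.86 | 2.05 | 2.38 |

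**Limits for Day 2 minus Day 1 from assay error alone, at 90 h**
- m = 1: 1.96·a·√(1 + 2.01²) = 1.96 × 2.246a. This is ±8.8% at a = 2%, ±22.0% at 5% and ±35.2% at 8%.
- m = 3: 1.96·a·√(1/3 + 1.345²) = 1.96 × 1.464a. This is ±5.7%, ±14.3% and ±22.9%.

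**What 8 pairs can show.** With 7 degrees of freedom, the 95% interval for the SD of the differences runs from √(7/16.01) = 0.66 to √(7/1.69) = 2.04 times the estimate. That is rough, but informative when nothing else is planned.

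**What a pooled within-subject CV would mean.** It averages two unequal variances. Relative to the Day 1 CV it equals √[(1 + ratio²)/2]. That is 1.48 to 1.61 for m = 1 and 1.64 to 1.83 for m = 3, so it overstates single-dose error by a factor of about 1.5 to 1.8. Any true change in PV over 24 h adds to this.

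**Double entry in the Nadler correlation.** The SAP does not say which Cohort 2 PV is correlated with Nadler. At an illustrative r = 0.80, the Fisher 95% interval is 0.22 to 0.96 for 8 subjects. It would shrink to 0.50 to 0.93 if both days were entered as 16 independent points.

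**The case against.** The study is exploratory and descriptive, and its repeatability aim is consistently about mGFR. Leaving PV out is a choice and contradicts nothing. That stands, so this is a missed use of collected data and not an error in the plan.

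A reader might infer that PV reproducibility is already a primary aim, because the third primary objective reads "To evaluate the PK of FD001 and FD003 in healthy subjects receiving 2 doses of VFI separated by 24 hours to evaluate the reproducibility" and FD003 is the PV marker. The sentence goes on to limit reproducibility to the mGFR technology, so it gives no support.

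A reader might also infer that the trial has no other evidence of FAST PV precision. It has some. Every cohort has serial FD003 samples after a single dose (15, 30, 60 and 120 minutes and later), and FD003 falls only about 1.5% in 2 hours at a 90 h half-life. Their scatter after dispersion reflects precision within one dose. It does not capture error across separate injections.

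The undefined change in PV in the SAP could be read as including Day 2 minus Day 1. However, the only PV change named as an endpoint is the one after the fluid challenge, and no SD or limits of agreement are planned. PV is also listed by subject (Listing 16.2.6.3.1), so a Day 2 mGFR shift could be checked by hand against that subject's PV. What is missing is a summary.

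**Conclusion.** The point holds as a low-cost improvement. Two FAST PVs per Cohort 2 subject are calculated, no endpoint or listed output pairs them, and the Nadler comparison cannot take their place. Day 2 PV error is about 1.8 to 2.05 times Day 1 with one sample and 2.1 to 2.4 times with three. These ratios rest on independent proportional assay error and the healthy-subject half-lives. Correlated assay error would lower them. The 125 h half-life in Section 3.4.3 belongs to severe renal impairment and does not apply to Cohort 2. The percentage limits also depend on the assumed 2-8% assay error.

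Two stronger readings should be resisted. One is to set these limits against the PV rise expected from the 350 mL albumin challenge. That challenge is in Cohort 1, within one dose and with no residual to subtract. The same model gives 1.96·√2·a/√m there, about ±14% (m = 1) or ±8% (m = 3) at an assumed a = 5%. The other is to treat the paired difference as FAST PV's single-dose error. It also contains carry-over subtraction and true 24 h change, so it is only an upper bound.

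The GFR repeatability endpoint has the companion gap: neither Protocol 10.5.2 nor SAP 10.1.10.2 specifies a Day 1/Day 2 analysis for it.

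**What to change.** 1. Add repeatability of FAST PV over 24 hours (Cohort 2) to Protocol 10.3.2.1 and SAP 5.4.1.
2. In Protocol 10.5.1 and SAP 10.1.10.1, report the within-subject Day 2 minus Day 1 PV difference in percent: mean with 95% CI, SD and limits of agreement. State the residual correction used. Label the result as an upper bound on method error that includes carry-over subtraction and true 24 h change, and not as single-dose error.
3. Use only the Day 1 PV in the Cohort 2 Nadler correlation and histogram, so that each subject enters once.
4. Define the change in plasma volume in SAP 10.1.10.1 by naming the two measurements compared.
5. Give the same Day 1/Day 2 table for mGFR under Protocol 10.5.2 and SAP 10.1.10.2, and add both tables to SAP Section 11.

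The cost is one endpoint line, a few sentences and a small paired table for each measure. All the data are already collected, and no extra samples or subjects are needed.
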